become invested in the patient's well-being which creates a closer, more supportive relationship. Alternatively, the friend may see this task as a burden and the relationship suffers. Our modified SAT model predicts that by (a) increasing YPLH's personal capabilities related to adherence (skills, knowledge, and beliefs), (b) providing greater access to clinic and peer adherence social support, and (c) positively altering their relationship and interactions (social interdependence) with an identified supportive person, problems with developmental transitions are overcome and adherence behavior is improved. In addition, while many individual and sociostructural contextual barriers to adherence such as emotional problems and access to transportation cannot fully be addressed with a Text-Based Adherence Game, mobile access to clinic staff who can provide referrals for services can help YPLH better overcome these barriers. Finally, the model suggests that when YPLH receive feedback on their HIV-related health outcomes, their motivation to engage in protective health behaviors is enhanced.

METHODOLOGY

This research will be divided into two phases: (1) a Development Phase (Aim 1: *Develop*) in which we will conduct formative research to guide development of a Text-Based Adherence Game and gain experience with its implementation in an iterative open trial and (2) a Randomized Controlled Pilot Phase (Aim 2; *Evaluate*). See Table 1 for Study Timeline.

Table 1: Study Timeline

Quarters	Year 1				Year 2				Year 3				Year 4			
	1	2	3	4	1	2	3	4	1	2	3	4	1	2	3	4
Aim 1: Develop																
Game/system creation	•	•	•													
Iterative trial			•	•	•											
Aim 2: Evaluate																
Recruitment			•	•	•											
Randomized pilot			•	•	•	•	•	•	•	•	•	•				
Analyses					•	•	•	•	•	•	•	•				

Inclusion criteria. Inclusion criteria for YPLH: Males and females living with HIV, 18 to 24 years old, will be eligible for enrollment in each phase of the study according to the following criteria: (1) read English *and* speak English or a local language spoken by clinic staff (e.g., Twi), (2) in medical care for HIV and receiving ART at our clinic, (3) aware of their HIV status as per clinical record, (4) not impaired by

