cognitive or medical limitations per clinician report, (5) possess a cellphone, and (6) able to give consent. *Adolescents living with HIV (ALH) between the ages 12-17 will also be eligible to participate in focus groups and cognitive interviews as part of a separate component of the Development Phase. Their eligibility criteria is as follows:* (1) *read English and speak English or a local language spoken by clinic staff (e.g., Twi),* (2) *in medical care for HIV and receiving ART at our clinic,* (3) *aware of their HIV status as per parent/guardian report,* (4) *not impaired by cognitive or medical limitations per clinician report,* (6) *able to give assent, and* (7) *their parent/guardian is able to give consent. Parents or guardians of ALH are also able to participate in focus groups and cognitive interviews as part of this separate component. Parent eligibility is as follows:* (1) *speak English or a local language spoken by clinic staff (e.g., Twi),* (2) *own a mobile phone,* (3) *aware of their child's HIV status,* (4) *not impaired by cognitive or medical limitations per clinician report, and* (6) *able to give consent.* Participants in the randomized pilot must have also demonstrated a recent detectable viral load. Study staff will NOT make changes to ART regimens and participants will be encouraged to speak with their doctor if they have concerns about their medications or side effects of these medications. Any unexpected ethical issues that arise with our participants will be discussed immediately with the PI. All participants will receive a resource packet including information on ART as well as references to local health and social services. We will also encourage participants to identify a treatment monitor to take part in the game. This will not be a requirement for our study, however, because those who begin playing the game without a monitor will be incentivized via game rewards to recruit one (and we will assess this occurrence). Participants without a monitor will be assigned a peer educator to fill this role. Inclusion criteria for treatment monitors includes: 1) *read English and speak English or a local language spoken by clinic staff,* (2) *target HIV patient has agreed to their participation,* (3) *aware of target patient's HIV status as per patient report,* (5) *possess a cellphone, and* (6) *able to give consent.*

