Exclusion criteria. Individuals will be excluded if they meet any of the following criteria: (a) self-reported participation in another ART adherence-related study (YPLH only) or (b) unable to understand the consent process.

Sample, site/recruitment, and retention. We will recruit 24 YPLH and potentially 24 treatment monitors for the iterative open trial, and between 5-40 YPLH for the youth advisory group, as part of the Development Phase. The advisory board ranges from 5-40 participants because those who attend the first group meeting will be invited back to attend two to four additional meetings. However, if they are unable to attend, new participants will be added to the group. *We will also recruit 12-16 ALH and 12-16 parents/guardians of ALH for focus groups and 10 parent-ALH dyads for cognitive interviews, as part of the Development Phase.* Sixty 60 YPLH, and potentially 30 treatment monitors, will be recruited for the pilot. In the pilot, it is estimated that 70% of youth will be female given that females account for 58% of all HIV cases in Ghana and seek treatment more than males (5). About 25% of YPLH will be newly-initiated to ART. Efforts will be made to equally sample young people who acquired HIV perinatally and behaviorally. Site/recruitment: Participants will be recruited from the HIV care clinic (the Clinic) at the Komfo Anokye Teaching Hospital (KATH), a teaching hospital affiliated with the Kwame Nkrumah University of Science and Technology (KNUST) located in Kumasi. It is the second largest clinic in the country and has a patient population estimated at 4,000. Although no research activities involving human subjects will occur at Rhode Island Hospital (RIH; the co-PI's institution), RIH will support KNUST and KATH with compliance on regulatory matters, including authoring the standard operating protocol, IRB applications and approvals, quality control, and data analysis. Retention techniques: routinely updating contact information, reminder phone calls, online monitoring of game interactions, maintaining records of friend/family contacts, and obtaining an emergency contact.

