Measures: Participants' overall satisfaction with the game will be assessed using a modified version of the Client Satisfaction Questionnaire (CSQ-8) after each iteration. The CSQ is an 8-item measure with good reliability and validity and used previously with African samples (46). They will also complete a modified Session Evaluation Form (SEF), which has 13 items that reflect areas of feasibility and intervention utility. Participants will complete measures of main study outcomes using an audio-assisted computer self-interview (ACASI). Main outcome measures are listed in the next section. The last prototype will be reviewed and revised by the research team before being finalized. **Training of Research Assistants (RAs), Fidelity Monitoring, and Supervision:** RAs will be trained by the co-PI ([name]) over a period of two days to provide

game instructions. Game instructions will be audio-recorded and coded for fidelity. Problems with fidelity will trigger retraining of RAs by the PI. Peer educators will receive in-person supervision from study staff who will themselves receive Skype supervision from the [name]. [name] will also monitor participants' game activity daily via the system's website.

Randomized Controlled Pilot Phase (Aim 2)

We will evaluate the preliminary impact of the Text-Based Adherence Game run for one year compared to a control group. The pilot will include 60 YPLH on ART with the same eligibility criteria as the open trial. The same procedures will also be used pending open trial feedback. The game will be evaluated via a baseline and two follow-up assessments (6-/12-months post-baseline). Randomization will occur after enrollment using a random number generator. Participants not randomized to the Text-Based Adherence Game will receive the SOC condition as described above. See Figure 4.

Figure 4. Steps for Aim 2 Randomized Controlled Pilot

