Medical or Professional Intervention in Event of Adverse Event. Although we do not anticipate any events in need of medical intervention associated with our study activities, due to our sample of YPLH we do recognize the need for some safeguards. All participants will be under the care of a physician as our study site is based in a public hospital HIV clinic and prescription of ART is an eligibility criteria of our study. All adverse events will be immediately reported to the PI. Serious adverse events will be reported to the KATH IRB, the KNUST IRB, and Rhode Island Hospital IRB as stipulated by the regulations of the IRB.

Potential Benefits of the Proposed Research to Participants and Others

There may be little or no direct benefit to participants from this study as this study is developing a novel text message program that may or may not improve adherence to HIV care for patient participants. However, reports from previous research have indicated that many participants feel that sharing information about their experiences of living with HIV or receiving HIV treatment with trained staff can be therapeutic. If requested, YPLH participants will be given information on HIV treatment, as well as referrals to local health and social services. Referrals to more intensive resources will be made as needed.

Importance of Knowledge to be Gained

This study will fill key gaps in scientific knowledge about the barriers and facilitators to HIV treatment adherence among YPLH in sub-Saharan Africa. Background literature suggests that this group has high rates of ART nonadherence, treatment attrition, and viral nonsuppression, and that these outcomes may be associated with the developmental transition from adolescence to adulthood. Additionally, the literature identifies key factors that influence ART adherence at the individual-, social-, and contextual-levels which can possibly be targeted through an engaging intervention using novel technology-based strategies. Thus, the risks of the proposed study are reasonable and balanced by the potential contribution of providing important information that can advance our knowledge of adherence to HIV care among

YPLH and whether the proposed intervention will improve adherence outcomes during this unique and vulnerable period of life.

Data and Safety Monitoring Plan

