1. “I usually eat at least 3 meals each day.” _____
2. “I am ready to start taking HIV medications.” _____
3. “Most of the people I live with know my HIV status.” _____
4. “I believe taking HIV medications can keep me healthy.” _____
5. “In the past 3 months, I found myself wishing I hadn't used street drugs so often.” _____
6. “Taking HIV medications would give me bad side effects.” _____
7. “I would know how to contact my pharmacist or medical provider if I had problems or questions about HIV medications.” _____
8. “I feel like I have a stable place to live.” _____
9. “If I don't take HIV medications exactly as instructed, the HIV in my body will become resistant to the medications.” _____
10. “I have a strong, trusting relationship with my medical provider.” _____
11. “Even though the time may vary on the weekends, I have a regular time when I wake up and go to bed.” _____
12. “I am anxious about my future because I have HIV.” _____
13. “I would know who and when to call for refills for HIV medications.” _____
14. “I sleep in the same bed almost every night.” _____
15. “I can cope with my HIV diagnosis.” _____
16. “Sometimes a homeless shelter is the only place I have to sleep.” _____
17. “Most of my family and friends know my HIV status.” _____
18. “My schedule is different every day.” _____
19. “Taking HIV medication would not really help me.” _____
20. “Even when it may be difficult, I will be able to let my medical provider know if I miss doses of HIV medications.” _____
21. “I regularly go to the clinic and meet with my medical provider.” _____
22. “HIV medications would be poison to my body.” _____
23. “I want to start taking HIV medications.” _____
24. “Despite having HIV, I can move forward with my life.” _____
25. “My household members who know I have HIV would help me remember to take my medication.” _____
26. “Taking HIV medications as prescribed would keep me from getting sick.” _____
27. “I feel supported by my family and friends when times are tough.” _____
28. “I would find it difficult to take pills at the same time every day.” _____

29. "I would take HIV medications even if they made me sick at first because the side effects would go away." _____

30. "My family and friends who know I have HIV would help me remember to take my medications." _____

31. "In the past 3 months, I found myself wishing I hadn't drunk alcohol so often." _____

32. "I know that I will be able to take all of my medication correctly." _____

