5. I feel guilty because I have HIV _____
6. Having HIV in my body is disgusting to me _____
7. People I know would treat someone with HIV as an outcast _____
8. People I know would be uncomfortable around someone with HIV _____
9. People I know believe that a person with HIV is dirty _____
10. People I know would reject someone with HIV _____
11. People I know would not want someone with HIV around their children _____
12. People I know think that a person with HIV is disgusting _____

Concerns about Disclosure Tool

Questions and Filters	Response

Indicate your agreement or disagreement with each statement:
 
a) I am very careful who I tell that I have HIV. _____
 
b) I don't feel the need to hide the fact that I have HIV. _____
 
c) I worry that people may judge me when they learn I have HIV. _____
 
d) Telling someone I have HIV is risky. _____
 
e) Since learning I have HIV, I worry about people discriminating against me. _____
 
f) It is easier to avoid new friendships than worry about telling someone that I have HIV. _____
 
g) I work hard to keep my HIV a secret. _____
	
1 Strongly Disagree
 
2 Disagree
 
3 Agree
 
4 Strongly Agree

Past 30-Day ART Adherence

Instructions

1. In the last 30 days, on how many days did you miss at least one dose of any of your HIV medication?

Write in number of days: _____ (0-30)

2. In the last 30 days, how good a job did you do at taking your HIV medication in the way you were supposed to? Very poor Poor Fair Good Very good Excellent

3. In the last 30 days, how often did you take your HIV medication in the way you were supposed to? Never Rarely Sometimes Usually Almost always Always

Antiretroviral Adherence: ACTG

List the medications you take for HIV.

Study Drug Name/Dose	# Pills Each Time (Pills Each Dose)	# Times Per Day (Doses Per Day)

The next section of the questionnaire asks about the study medications that you may have missed taking over the last four days. Please complete the following table below.

**IF YOU TOOK ONLY A PORTION OF A DOSE ON ONE OR MORE OF THESE DAYS,
PLEASE REPORT THE DOSE(S) AS BEING MISSED.**

Step 1 Names of your anti-HIV study drugs	HOW MANY DOSES DID YOU MISS				
	Step 2 Yesterday	Step 3 Day before yesterday (2 days ago)	Step 4 3 days ago	Step 5 4 days ago	—
	• doses	• doses	• doses	• doses	
	• doses	• doses	• doses	• doses	

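### Two treatment-readiness items ask patients already receiving ART about starting it, and the four-day adherence table asks about study drugs the trial does not supply

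*Combined protocol and SAP*

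**What the plan says.** Eligibility is consistent on treatment status. The inclusion criteria in the Methodology require young people to be "in medical care for HIV and receiving ART at our clinic". The Randomized Controlled Pilot Phase section repeats this: "The pilot will include 60 YPLH on ART with the same eligibility criteria as the open trial". The section on medical intervention for adverse events says that "prescription of ART is an eligibility criteria of our study". The sampling section adds "About 25% of YPLH will be newly-initiated to ART", so the newest patients have also begun treatment. The pilot has one further condition: "Participants in the randomized pilot must have also demonstrated a recent detectable viral load".

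Appendix 3 contains the HTRM. Its main block has 37 statements rated from 1 (strongly disagree) to 5 (strongly agree). Item 2 is "I am ready to start taking HIV medications" and item 23 is "I want to start taking HIV medications". Appendix 3 gives no skip rule and no response option for someone already on treatment.

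The four-day AACTG adherence measure appears under Primary Outcomes in the Measures section. Its table in Appendix 3 asks for missed doses of study medications, with a first column headed "Names of your anti-HIV study drugs". Another column, in the list of current medicines above it, is also labelled as study drug. The trial tests a text-message game. The protocol describes no study drug, and study staff will not change regimens.

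**The concern.** Items 2 and 23 presuppose that the respondent has not begun treatment. In an enrolled patient the same response can mean different things. Disagreement may mean unwillingness, or only that treatment began long ago. Agreement may mean commitment, goodwill, or an intention to resume after a lapse. An item whose meaning differs between patients, or within a patient between visits, adds noise to a change score.

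It could also push in the wrong direction. The pilot enrols patients with a recent detectable viral load, so some may read 'start' as 'restart' at baseline. If such a patient's adherence then improves, an honest answer could move from agree to disagree. Hypothesis Two tests differences over time on each outcome variable, so this would matter for any analysed score that contains the two items.

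The AACTG wording raises a smaller version of the same problem in a primary-outcome measure. A patient who takes no study drug may not be sure which medicines the table covers.

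**Working it through.** The plan states no figure on this point, so there is none to reproduce. The check compares texts and counts items.

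**1. Treatment status.** The three eligibility statements and the sampling statement all place enrolled young people on ART. None describes a patient who has yet to begin.

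**2. Count of the 37 agree/disagree HTRM items.**
- Wording about starting: items 2 and 23. 2/37 = 5.4%.
- Conditional 'would' wording: items 6, 7, 13, 19, 22, 25, 26, 28, 29, 30, 36 and 37, which is 12 items.
- Neither: 37 − 2 − 12 = 23 items, or 62.2%.

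The two groups together make 14/37 = 37.8%, but they are not equally affected. Only items 2 and 23 presuppose that treatment has not begun. Items 7 and 13 (whom to contact about problems or refills) and items 25 and 30 (others helping the patient to remember) can be answered directly by someone on ART. Items such as 6 and 22 are awkward but answerable.

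**3. Possible weight in a score.** The visible text gives no HTRM scoring rule, total or subscale. As an assumption, take a simple sum of the 37 items scored 1 to 5:
- range = 37 × (5 − 1) = 148 points;
- the two items' share = 2 × 4 = 8 points;
- 8/148 = 5.4%.

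The distortion for one patient therefore lies between 0 and 8 points. The upper end needs the most extreme misreading of both items. The sum ignores any reverse scoring and the HTRM's further blocks on other response scales. For a subscale of k equally weighted items containing both, the share is 2/k, which exceeds 5.4% whenever k is below 37.

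**4. AACTG wording.** The section opens by asking the patient to list their HIV medicines. The column beneath and the missed-dose table then use study-drug terms, and later questions in the same instrument speak of anti-HIV medications. The 30-day adherence items, also a primary-outcome measure, refer to the patient's own HIV medication. The terms are inconsistent, and the documents give nothing from which to estimate an effect on recorded adherence.

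**5. Does the plan already deal with it?** The Measures section allows revisions, based on formative work, for cultural relevance. The pilot procedures carry over subject to open-trial feedback. Neither provision mentions treatment status. A change is not ruled out, but none is planned.

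**The case against.** The strongest reply is that this concerns two items in a long questionnaire. Readiness is asked elsewhere in suitable terms: the Motivational Readiness measure has a 1 to 10 rating of readiness to take medication as prescribed. Secondary outcomes are described in Figure 5, which is not shown, so it cannot be established that an HTRM total is analysed. Both arms receive the same wording at every assessment, so the likely result is noise and not a biased contrast. All of this stands and limits the importance of the point. It does not make items 2 and 23 interpretable.

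A reader might infer that the whole HTRM score is unreadable, or that it cannot register improvement from the game. The documents do not support that. Of the 37 items, 35 do not presuppose an untreated patient. They include items the game could plausibly affect, such as provider trust, clinic attendance, support and taking medication correctly. Counting all 14 'start' and 'would' items as defective would also go too far. Appendix 3 uses 'would' in measures plainly written for treated patients, and changing the tense of the 12 conditional items is a matter of preference.

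A reader might also infer that the AACTG wording will inflate or lose primary-outcome data. That is conjecture. The opening request to list HIV medicines gives 'study drug' a sensible meaning in context, and items are read out by computer with staff present to help. What remains is that the wording is inconsistent and easily corrected.

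**Conclusion.** The mismatch is real and small. HTRM items 2 and 23 do not fit a population required to be receiving ART, and answers to them would add noise, possibly wrong-direction change, to any readiness score that includes them. They are 2 of 37 items: 5.4% of the range under an assumed simple sum, and a larger share of any shorter subscale that contains both. The direction of any net effect cannot be predicted from the documents.

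The study-drug wording in the AACTG table is avoidable confusion of unknown size in a primary-outcome measure. Nothing here bears on clinic visits, viral load, CD4 count or the power statement. The conclusion rests on the eligibility text and the items as printed in Appendix 3. It assumes that no adapted wording or scoring rule exists outside the visible text. This is a cheap improvement and not a threat to the trial's conclusions.

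**What to change.** Before data collection:

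- Reword HTRM items 2 and 23 to refer to continuing HIV medication, or exclude both from any HTRM total or subscale by a rule written down in advance. State the HTRM scoring in the same place so that the rule has something to attach to.
- In the AACTG section, replace 'study medications', 'study drugs' and 'Study Drug Name' with 'your HIV medications'.
- Keep the wording identical across arms and assessments.

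If collection has already begun, do not change items 2 and 23 midway. Exclude them by a rule fixed before any comparison of the arms. By the same reasoning, leave the AACTG text as it is and record its wording as a limitation.

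The cost is a few edits to the computer-interview script and a slight departure from the source instruments, which makes comparison with other users of those instruments a little less exact. Excluding items 2 and 23 avoids the departure for the HTRM items themselves but leaves a score two items short of the full set.

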1	
By oral sex we mean, have you ever put your mouth on anyone else's penis/vagina or has anyone else put his/her mouth on your vagina/private parts. By vaginal sex, we mean has anyone ever put his penis into your vagina/private part. By anal sex we mean, has anyone ever put his penis in your anus/butt.
 
Have you ever had sexual intercourse of any kind (oral, vaginal or anal)?
	
1= Yes 2= No [Skip]

2	
The very last time you had sex, did you use a condom?
	
1= Yes 2= No

3	
Have you ever had oral sex? (By "oral sex" we mean, have you ever put your mouth on anyone else's vagina/penis or has anyone else put his/her mouth on your vagina/private parts?)
	
1= Yes 2= No [Skip]

4	
In the past 120 days, have you had oral sex (mouth on privates)?
	
1= Yes 2= No [Skip]

5	
In the past 120 days, how many times have you had oral sex (mouth on privates)?
	    (Range 1-999)
6	
In the past 120 days, when you had oral sex (mouth on privates), how many times did you use a condom (rubber) or dental dam?
	    (Range 0-999)
7	
Have you ever had vaginal sex? (By "vaginal sex," we mean when a man puts his penis in a woman's vagina.)
	
1= Yes 2= No

8	
In the past 120 days, have you had vaginal sex (penis in vagina)?
	
1= Yes 2= No [Skip]

9	
In the past 120 days, how many times have you had vaginal sex (penis in vagina)?
	    (Range 1-999)
10	
In the past 120 days, when you had vaginal sex (penis in vagina), how many times did you use a condom ?
	  
11	
Have you ever had anal sex? (By "anal sex," we mean when a man puts his penis in someone's anus or butt.)
	
1= Yes 2= No

12	
In the past 120 days, have you had anal sex (penis in butt)?
	
1= Yes 2= No [Skip]

13	In the past 120 days, how many times have you had anal sex (penis in butt)?	     (Range 1-999)

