81	In the last 120 days, how many days did you use marijuana?	   (Range 1-99)
82	In the last MONTH, how many times did you use marijuana?	   (Range 1-99)
83	When was the last time you used any marijuana?	1=Within the past week 2=2 weeks ago 3=3-4 weeks 4=More than 4 weeks ago
84	With whom have you smoked marijuana? Check all that apply.	1=Parent 2=Brother/Sister 3=Other Relative 4=Friend 5=Boyfriend/Girlfriend 6=Teacher/Coach 7=Therapist 8=Acquaintance 9=By myself
95	Have you ever used methphetamines (speed)?	1=Yes 2=No
96	How old were you when you first started using methphetamines?	   (Range 1-99)
97	In the past 120 days, have you used methphetamines?	1=Yes 2=No
98	How many days in the past 120 days did you use methphetamines?	   (Range 1-99)
99	How many days in the past 30 days have you used methphetamines?	   (Range 1-99)
100	Have you ever used any type of cocaine (coke, powder, crack, or freebase)?	1=Yes 2=No
101	How old were you when you first started using any type of cocaine (coke, powder, crack, or freebase)?	   (Range 1-99)
102	In the past 120 days, have you used any type of cocaine (coke, powder, crack or freebase)?	1=Yes 2=No
103	How many days in the past 120 days did you use any type of cocaine (coke, powder, crack, or freebase)?	   (Range 1-99)
104	How many days in the past 30 days have you used any type of cocaine (coke, powder, crack, or freebase)?	   (Range 1-99)

		1=Within the past week 2=2 weeks ago 3=3-4 weeks 4=More than 4 weeks ago
105	When was the last time you used any type of cocaine (coke, powder, crack, or freebase)?	
110	Have you ever used club drugs (ecstasy "x", Special K, etc.)?	1=Yes 2=No
111	How old were you when you first started using club drugs (ecstasy "x", Special K, etc.)?	   (Range 1-99)
112	In the past 120 days, did you use club drugs (ecstasy, "x", Special K, etc.)?	

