113	How many days in the past 120 days did you use club drugs (ecstasy "x", Special K, etc.)?	   (Range 1-99)
114	How many days in the past 30 days have you used a club drug (ecstasy "x", Special K, etc.)?	   (Range 1-99)
115	When was the last time you used a club drug (ecstasy "x", Special K, etc.)?	1=Within the past week 2=2 weeks ago 3=3-4 weeks 4=More than 4 weeks ago
116	Have you ever used over the counter or prescription medication to get high (cough syrup, Ritalin, Oxycontin, Vicodin, etc.)?	1=Yes 2=No
117	How old were you when you first started using over the counter or prescription medication to get high (cough syrup, Ritalin, Oxycontin, Vicodin, etc.)?	   (Range 1-99)
118	In the past 120 days, have you used over the counter or prescription medication to get high (cough syrup, Ritalin, Oxycontin, Vicodin, etc.) days?	1=Yes 2=No
119	In the past 120 days, how many times did you use over the counter or prescription medication to get high (cough syrup, Ritalin, Oxycontin, Vicodin, etc.)?	   (Range 1-99)
120	How many days in the past 30 days have you used over the counter or prescription medication to get high (cough syrup, Ritalin, Oxycontin, Vicodin, etc.)?	   (Range 1-99)
121	When was the last time you used any type of over the counter medication or prescription medication to get high (cough syrup, Ritalin, Oxycontin, Vicodin, etc.)?	1=Within the past week 2=2 weeks ago 3=3-4 weeks 4=More than 4 weeks ago
122	Have you ever used heroin (smack, junk, or China White)?	1=Yes 2=No
123	In the past 120 days, have you ever used heroin (smack, junk, China White)?	1=Yes 2=No
124	In the past 120 days, how many times did you inject heroin?	   (Range 1-99)
125	In the past 30 days, how many times did you inject heroin?	   (Range 1-99)
126	How important is it for you NOT to use drugs? (pick a number from 1-10)	1=Not important 5=Somewhat important 10=Very important

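### As printed, some risk-behaviour items in Appendix 3 leave certain respondents without a correct answer: the item 1 definitions miss insertive partners, several counts have no zero, and four 120-day counts stop at 99.

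*Combined protocol and SAP*

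**What the plan says.** The module is part of the Appendix 3 questionnaire. Under Assessments, the protocol has assessments administered by audio computer-assisted self-interview (ACASI) at baseline, 6 months and 12 months. Both sexes are eligible.

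**Item 1.** The definitions come before the question. Vaginal sex: "By vaginal sex, we mean has anyone ever put his penis into your vagina/private part". Anal sex: "By anal sex we mean, has anyone ever put his penis in your anus/butt". Oral sex is defined for both giving and receiving. A No answer carries a skip instruction with no destination. Item 7 defines vaginal sex without reference to role ("we mean when a man puts his penis in a woman's vagina"), and item 11 does the same for anal sex, but both come after item 1.

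**Short-window counts.** Item 99 asks "How many days in the past 30 days have you used methphetamines" and prints a range of 1-99. Items 104, 114 and 120 ask the same 30-day question for cocaine, club drugs and misused medication, with the same range. Item 82 (times marijuana was used in the last month) and items 124-125 (heroin injections, 120 and 30 days) also print 1-99. Item 124 reads "In the past 120 days, how many times did you inject heroin".

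**120-day day counts.** Item 81 asks "In the last 120 days, how many days did you use marijuana" with a range of 1-99. Items 98, 103 and 113 use the same range for methamphetamines, cocaine and club drugs.

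By contrast, condom-use items 6 and 14 print 0-999.

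**The concern.** A structured interview needs a valid response for every true state. Here some respondents have none. A man who applies item 1's definitions literally may have to deny sexual experience that he has had. A person who last used cocaine two months ago can truthfully report use in the past 120 days, but then cannot enter 0 for the past 30. A person who uses heroin without injecting cannot enter 0 injections. A daily user cannot enter 120.

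In each case the respondent must enter a false value, leave a blank, or leave the module. The same form is used at three visits, so the distortion could recur and could blur change over time on these items. The form is clearly meant for men: it asks about female partners (items 18-19 and 23-24) and about having made someone pregnant (item 35). The item 1 wording therefore conflicts with the module's own later items.

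**Working it through.** The plan states no figure to reproduce. The check sets each printed rule beside the answers that can be true.

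**1. Item 1 and men**

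- Acts that qualify for Yes under the printed definitions: receptive vaginal sex, receptive anal sex, and giving or receiving oral sex.
- Acts that do not qualify: insertive vaginal sex and insertive anal sex.
- A literal No despite sexual experience therefore needs a man with insertive vaginal or anal sex only, and no oral or receptive anal sex.
- Number of men who meet the wording: the Sample, site/recruitment, and retention section says "In the pilot, it is estimated that 70% of youth will be female". Expected men = (1 - 0.70) x 60 = 18. This is how many are exposed to the wording, not how many are misclassified.

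**2. Counts over 30 days or the last month**

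- True values for a 30-day day count: 0 to 30. Printed range: 1 to 99.
- True values that cannot be entered: 0.
- Impossible values that can be entered: 31 to 99, which is 99 - 30 = 69 values.
- Zero is needed even if a No at the 120-day screener skips the block, because a person whose last use was 31 to 120 days ago correctly answers Yes there.
- Item 82 has the same missing zero. Items 124-125 follow a screener on any heroin use, so a Yes does not imply injection.

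**3. Day counts over 120 days**

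- True maximum 120, printed maximum 99.
- Daily user: 120 - 99 = 21 days lost; 21/120 = 17.5%.
- Whether 0 is also needed depends on routing. A Yes at the screener rules out 0. However, the drug screeners print no skip on No, and respondents are told to answer all questions. If No does not skip, 0 is needed here too.

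**4. What the module recovers elsewhere**

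| Substance | Count with no 0 | Last-use item with an option beyond four weeks |
|---|---|---|
| Marijuana | 82 | 83 |
| Cocaine | 104 | 105 |
| Club drugs | 114 | 115 |
| Medication | 120 | 121 |
| Methamphetamines | 99 | none follows |
| Heroin injection | 124, 125 | none follows |

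The cigarette and alcohol items are not used here, because their printed ranges cannot be matched to the questions with confidence.

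**The case against.** The best defence is that the practical harm is small.

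- **Item 1.** The question itself is general: "Have you ever had sexual intercourse of any kind (oral, vaginal or anal". Many men with insertive experience will simply answer Yes, and any man with oral sex meets the definition. This stands. A reader might infer that men's sexual-risk data are lost at every visit; the documents do not support that. They show a risk of misrouting for one subgroup, and they do not say where the skip leads.
- **Stopping use.** A reader might infer that a participant who stops cannot be recorded as having stopped. That is too strong. Anyone abstinent for 120 days answers No at the screener, and items 83, 105, 115 and 121 record last use more than four weeks ago. The treatment readiness measure in Appendix 3 also asks about drug use over three months with a never option. What remains is that the counts themselves would be wrong or blank, and that no last-use item follows item 99.
- **Enforcement.** The protocol names ACASI but gives no validation or correction rules, and Appendix 3 has staff present to assist. It is therefore an inference that the program would enforce the printed ranges and that errors could not be corrected.
- **Relevance.** The primary outcomes are adherence, clinic visits and biologic measures. The background does not name substance use as a reason for the trial, and the readable text plans no analysis specific to these items. Figure 5, which describes the secondary outcomes, is not available. This stands and limits the weight of the point.
- **Later revision.** The Measures paragraph allows measures to be revised after formative work, but for cultural relevancy. That permits a correction without committing anyone to review skips and ranges.

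**Conclusion.** The point holds for the named items and is minor. Item 1 gives a literal-minded man with only insertive vaginal or anal experience no correct route. Up to about 18 of 60 participants meet that wording, on the protocol's own estimate of the sex split; how many would be misrouted cannot be estimated from the documents. Seven counts (82, 99, 104, 114, 120, 124, 125) lack a needed zero, and four of them (99, 104, 114, 120) accept 31 to 99 days in a 30-day window. Four 120-day counts (81, 98, 103, 113) understate a daily user by 21 days, or 17.5%.

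This rests on the form being programmed as printed. It does not extend to the module as a whole: the sex-act counts at items 5 and 13 (1-999) and the condom counts at items 6 and 14 (0-999) are adequate. Only non-primary self-report data are affected.

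**What to change.** Before the pilot baseline interview is programmed:

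1. Replace the vaginal and anal definitions in item 1 with the role-neutral wordings already used at items 7 and 11, and print the skip destination.
2. Set the 30-day day counts (99, 104, 114, 120) to 0-30.
3. Set the 120-day day counts (81, 98, 103, 113) to 0-120, or to 1-120 if a No at the screener is programmed to skip them. Print that skip if so.
4. Allow 0 on the counts of times (82, 124, 125), for example 0-999 to match items 6 and 14.

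The cost is a small amount of reprogramming and a revised Appendix 3, with no added participant burden. Open-trial answers on these items would not be directly comparable with pilot answers. Making the change before baseline keeps all three pilot visits on one form.
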